21.1. Reportable Events by Investigational Site to Boston Scientific

Any device-related, procedure-related, or pelvic floor-related adverse event experienced by the study subject after informed consent and once considered enrolled in the study, whether during or subsequent to the procedure, must be recorded in the CRF.

Refer to Section 19 (Potential Risks and Benefits) for the known risks associated with the study device(s).

Definitions of the adverse events included in the secondary endpoint will match the definitions created for the AUGS PFD Registry. All event definitions will be provided to the sites as part of a dictionary in the Manual of Operations.

When possible, the medical diagnosis should be reported as the Event Term instead of individual symptoms.

If it is unclear whether or not an event fits one of the above categories, or if the event cannot be isolated from the device or procedure, it should be submitted as an adverse event and/or device deficiency.

Underlying diseases are not reported as AEs unless there is an increase in severity or frequency during the course of the investigation. Death should not be recorded as an AE, but should only be reflected as an outcome of a specific SAE (see Section 21.2 for AE definitions).

21.2. Definitions and Classification

Adverse event definitions are provided in Table 21.2-1. Administrative edits were made to combine definitions from ISO 14155:2011 (Clinical investigation of medical devices for human subjects - Good clinical practice) and MEDDEV 2.7/3 12/2010.

Table 21.2-1: Adverse Event Definitions

Term	Definition
Adverse Event (AE) Ref: ISO 14155:2011 Ref: MEDDEV 2.7/3 12/2010	Any untoward medical occurrence, unintended disease or injury, or any untoward clinical signs (including an abnormal laboratory finding) in subjects, users or other persons, whether or not related to the investigational medical device. NOTE 1: This includes events related to the investigational medical device or comparator. NOTE 2: This definition includes events related to the procedures involved (any procedure in the clinical investigation plan). NOTE 3: For users or other persons, this definition is restricted to events related to the investigational medical device.

Table 21.2-1: Adverse Event Definitions

Term	Definition

Serious Adverse Event (SAE)
 
Ref: ISO 14155:2011 Ref: MEDDEV 2.7/3 12/2010
	
Adverse event that:
 
 • Led to death, • Led to serious deterioration in the health of the subject, that either resulted in: 
 – a life-threatening illness or injury, or – a permanent impairment of a body structure or a body function, or – in-patient or prolonged hospitalization of existing hospitalization, or – medical or surgical intervention to prevent life-threatening illness or injury or permanent impairment to a body structure or a body function • Led to fetal distress, fetal death, or a congenital abnormality or birth defect. 
NOTE: Planned hospitalization for a pre-existing condition, or a procedure required by the clinical investigational plan, without serious deterioration in health, is not considered a serious adverse event.

Device Deficiency
 
Ref: ISO 14155:2011 Ref: MEDDEV 2.7/3 12/2010
	
A device deficiency is any inadequacy of a medical device with respect to its identity, quality, durability, reliability, safety or performance.
 
NOTE: Device deficiencies include malfunctions, misuse or use errors, and inadequate labeling.

Abbreviations: EC=Ethics Committee; IRB=Institutional Review Board

21.3. Relationship to Study Device (Mesh Cohort Only)

The investigator must assess the relationship of the AE to the study device as related or unrelated. See criteria in Table 21.3-1:

Table 21.3-1: Criteria for Assessing Relationship of Study Device to Adverse Event

Classification	Description

Unrelated (Not Related)
	
 • The adverse event is determined to be due to a concurrent illness or effect of another device/drug and is not related to the investigational product.

Related (Possible, Probable or Definite)
	
 • The adverse event is determined to be potentially related to the investigational product, and an alternative etiology is equally or less likely compared to the potential relationship to investigational product, or • There is a strong relationship to investigational product, or recurs on re-challenge, and another etiology is unlikely, or • There is no other reasonable medical explanation for the event.

21.4. Relationship to Study Delivery Device (Mesh Cohort Only)

The investigator must assess the relationship of the AE to the study delivery device as related or unrelated. See criteria in Table 21.4-1:

Table 21.4-1: Criteria for Assessing Relationship of Study Delivery Device to Adverse Event

Classification	Description
Unrelated (Not Related)	
 The adverse event is determined to be due to a concurrent illness or effect of another device/drug and is not related to the investigational product.
Related (Possible, Probable or Definite)	
 The adverse event is determined to be potentially related to the investigational product, and an alternative etiology is equally or less likely compared to the potential relationship to investigational product, or There is a strong relationship to investigational product, or recurs on re-challenge, and another etiology is unlikely, or There is no other reasonable medical explanation for the event.

21.5. Relationship to Study Procedure

The investigator must assess the relationship of the AE to the study procedure as unrelated, possibly related, probably related, or definitely related. See criteria in Table 21.5-1.

Table 21.5-1: Criteria for Assessing Relationship to Study Procedure

Classification	Description
Unrelated (Not Related)	
 No evidence that the timing of the adverse event has a relationship to the study procedure performed.
Possibly Related	
 The adverse event has a timely relationship to the study procedure performed. However, a potential alternative etiology may be responsible for the adverse event.
Probably Related	
 The adverse event has a timely relationship to the study procedure performed and the causative relationship can be clearly established. No potential alternative etiology is apparent.
Definitely Related	
 The adverse event has a timely relationship to the study procedure performed and the causative relationship can be clearly established. No potential alternative etiology is apparent. There is no other reasonable medical explanation for the event.

21.6. Relationship to Pelvic Floor

The investigator must assess the relationship of the AE to the pelvic floor as unrelated or related. See criteria in Table 21.6-1.

Table 21.6-1: Criteria for Assessing Relationship to Pelvic Floor

Classification	Description
Unrelated	
 No evidence that the adverse event has a relationship to the pelvic floor and supporting tissues.
Related	
 The adverse event is determined to be potentially related to the pelvic floor and supporting tissues including but not limited to lacerations, avulsions, tears, pelvic organ prolapse (cystocele, rectocele, enterocele, uterine, rectal), urinary incontinence (stress, urge), urinary voiding dysfunction (retention, obstructed voiding, incomplete emptying), fecal incontinence (urgency, irritable bowel syndrome), defecatory dysfunction (constipation, obstipation, stool trapping, IBS), pain (dyspareunia, pelvic, perineal), and infection (bladder, urinary tract, vaginal). There is a strong relationship to the pelvic floor and supporting tissues, and another etiology is unlikely, or There is no other reasonable medical explanation for the event.

21.7. Investigator Reporting Requirements

The communication requirements for reporting to BSC are as shown in Table 21.7-1.

Table 21.7-1: Investigator Reporting Requirements

Event Classification	Communication Method	Communication Timeline
Serious Adverse Events related to the study device, procedure and/or pelvic floor or events resulting in death regardless of relationship to the device, procedure or pelvic floor.	Complete AE CRF page with all available new and updated information.	
 Within 2 business days of first becoming aware of the event or as per local/regional regulations. Reporting required through the end of the study.
	If requested by Sponsor, provide all relevant source documentation (unidentified) for the reported event.	
 When documentation is available

Table 21.7-1: Investigator Reporting Requirements

Event Classification	Communication Method	Communication Timeline

Adverse Events related to the study device and/or procedure. Events assessed for reporting shall include but are not limited to:
 
 • Pelvic pain • Infection (by type) • De novo dyspareunia • Vaginal shortening • Vaginal scarring • De novo vaginal bleeding • Atypical vaginal discharge • Fistula formation • De novo voiding dysfunction (including de novo incontinence) • Neuromuscular problems (including groin and leg pain) • Revision/re-surgery • Recurrent prolapse • Mesh exposure • Mesh erosion 	
Complete the AE CRF page, which contains such information as onset date of the AE, treatment provided if any, resolution, assessment of seriousness, and relationship to study device.
	
 • In a timely manner (e.g., recommended within 10 business days of first becoming aware of the event). • Reporting required through end of subject participation.

Adverse Events related to the pelvic floor. Events assessed for reporting shall include but are not limited to:
 
 • Urinary tract infections • Pelvic organ prolapse • Urinary incontinence • Fecal incontinence • Pelvic Pain 	
Complete the AE CRF page, which contains such information as onset date of the AE, treatment provided if any, resolution, assessment of seriousness, and relationship to study device.
	
 • In a timely manner (e.g., recommended within 10 business days of first becoming aware of the event). • Reporting required through end of subject participation.

Device Deficiencies (including but not limited to failures, malfunctions, and product nonconformities) NOTE: Any Investigational Device Deficiency that might have led to a serious adverse event if a) suitable action had not been taken or b) intervention had not been made or c) if circumstances had been less fortunate is considered a reportable event.
	
Complete CRF with all available new and updated information.
	
 • Within 1 business day of first becoming aware of the event. • Reporting required through the end of the study.

Abbreviations: AE=adverse event; CRF=case report form

21.8. *Boston Scientific Device Deficiencies*

All device deficiencies (including but not limited to complications, malfunctions, use errors, product nonconformities, and labeling errors) will be documented and reported to Boston Scientific. If possible, the device(s) should be returned to BSC for analysis. Instructions for returning the device(s) will be provided. If it is not possible to return the device, the investigator should document why the device was not returned and the final disposition of the device. Device failures and malfunctions should also be documented in the subject's medical record.

Device deficiencies (including but not limited to failures, malfunctions, and product nonconformities) are not to be reported as adverse events. However, if there is an adverse event that results from a device failure or malfunction, that specific event would be recorded on the appropriate CRF.

Any Device Deficiency that might have led to a serious adverse event if a) suitable action had not been taken or b) intervention had not been made or c) if circumstances had been less fortunate is considered a reportable event.

21.9. *Reporting to Regulatory Authorities / IRBs / ECs / Investigators*

Boston Scientific is responsible for reporting adverse event information to all participating investigators and regulatory authorities, as applicable.

The Principal Investigator is responsible for informing the IRB/EC, and regulatory authorities of an SAE as required by local/regional regulations.

22. Committees

22.1. *Safety Monitoring Process*

To promote early detection of safety issues, an internal Safety Monitoring Team will provide evaluations of safety events. Success of this program requires dynamic collection of unmonitored data as soon as the event is reported. This is expedited through Boston Scientific's Safety Office, which is responsible for coordinating the collection of information for the subject dossier from the centers. During regularly scheduled monitoring visits, clinical research monitors will support the dynamic reporting process through their review of source document information.

23. Suspension or Termination

23.1. *Premature Termination of the Study*

Boston Scientific reserves the right to terminate the study at any stage but intends to exercise this right only for valid scientific or administrative reasons and reasons related to protection of subjects. Investigators, associated IRBs/ECs, and regulatory authorities, as applicable, will be notified in writing in the event of study termination.

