11.4.7. Months 6, 12, 18, 24, 36 Visits (-4/+12 weeks)

- Pelvic exam with vaginal length measurement
- Assessment of infection (vaginal, bladder)
- Prolapse grading (POP-Q Scoring)
- Assessment of pain (TOMUS pain scale) and analgesic intake
- PFDI-20
- PFIQ-7
- PISQ-12

- PGI-I for Prolapse
- SSQ-8 for surgical satisfaction (Months 6, 12, 24, 36 only)
- EQ-5D for health status (Months 12, 24, 36 only)
- Assessment of adverse events (device, procedure, or pelvic floor related)
- Assessment of risk factors
- Study completion (Month 36 only)

All subjects who have completed the study surgery and discharge will proceed to be followed through the above-outlined study visits to Month 36 where the primary endpoint analysis will be achieved when the last subject completes this visit. All subjects completing the Month 36 visit will be considered to have completed the study.

11.5. *Re-Intervention/Re-Surgery*

It is the intention of this study to demonstrate an improvement in anterior/apical pelvic organ prolapse through clinical effectiveness of a transvaginal prolapse repair kit. However, it is recognized that during the course of the study, there is a possibility subjects may require a medical re-intervention for events including but not limited to failed prolapse repair, persistence of prolapse symptoms, or a mesh or procedure-related complication. A re-intervention may include surgical or non-surgical treatments and can occur for a medical complication or for prolapse recurrence. For the purpose of this study surgical interventions shall be classified as “re-surgery” and non-surgical interventions shall be classified as “re-interventions”. Analyses will be performed to compare the rate of office-based interventions and of surgical interventions for medical complications and for prolapse recurrence in both treatment groups.

Non-surgical interventions (re-interventions) are defined as office-based procedures and do not involve an operating room procedure. Examples of non-surgical interventions may include but are not limited to an office visit to trim exposed mesh or suture in the vagina, a pessary, or physical therapy to treat procedural complications or persistent prolapse symptoms. Data on non-surgical interventions will be captured in the CRFs. Subjects will continue to be followed per the regular study visit schedule.

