12.1.1.1. Hypotheses

Superiority testing for effectiveness will be performed for the primary hypothesis.

Statistical testing will be performed to determine if composite endpoint of anatomic and symptomatic success rate in transvaginal mesh repair (treatment) group will be superior to traditional native tissue repair (control) group. The null hypothesis is that the success rate in treatment group is less than or equal to the success rate in control group:

$$H_0: \pi_{treatment} - \pi_{control} \leq 0$$

The alternative hypothesis is:

$$H_a: \pi_{treatment} - \pi_{control} > 0$$

where $\pi_{treatment}$ and $\pi_{control}$ is the probability of success in treatment group and control group respectively. The rejection of null hypothesis indicates the superiority of the treatment group over the control group.

Statistical testing will be performed to determine if the overall complication rate (i.e. serious adverse device effects and serious procedure-related adverse events) of treatment group is non-inferior to the control group. The null hypothesis is that the complication rate in treatment group is greater than or equal to the rate in control group plus margin:

$$H_0: \pi_{treatment} - \pi_{control} \geq \Delta$$

The alternative hypothesis is:

$$H_a: \pi_{treatment} - \pi_{control} < \Delta$$

where $\pi_{treatment}$ and $\pi_{control}$ are the overall complication rate in treatment group and control group respectively, and $\Delta > 0$ is defined as the non-inferiority margin.

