12.1.1.2. Sample Size

The statistical power calculation is based on a superiority assumption with a binary primary outcome. Success, based on a composite endpoint of anatomic and symptomatic success at 36 month is assumed to be 70.0% for the native tissue arm and 85.0% for transvaginal mesh arm.¹⁷⁻²¹ With 2-sided type I error of 0.05 and type II error of 0.1 (power 90%), 316 subjects (158 subjects per arm) are needed to detect 15% difference of transvaginal mesh to native tissue repair. In addition to a superiority assumption, statistical testing will be performed for non-inferiority using a margin of -12%.

To assess for safety, the overall complication rate (i.e. serious adverse device effects and serious procedure-related adverse events) is anticipated to be approximately 14%.²² With type I error of 0.05 and type II error of 0.20 (power 80%), 298 subjects (149 subjects per arm) are needed to detect non-inferiority with a margin of 10%.

To assess for office-based interventions for complications, the rate is anticipated to be approximately 2%.²² With type I error of 0.025 and type II error of 0.10 (power 90%), 330 subjects (165 subjects per arm) are needed to detect non-inferiority with a margin of 5%.

To assess for of surgical intervention for complications, the rate is anticipated to be approximately 1%.²² With type I error of 0.025 and type II error of 0.10 (power 90%), 260 subjects (130 subjects per arm) are needed to detect non-inferiority with a margin of 4%.

Non-surgical subjects will be enrolled by the PFD Registry and analyzed in this clinical study. Non-surgical subjects will not be enrolled into this clinical study. Using the above calculations and assuming a 20% loss to follow-up rate, a total of 414 subjects (207 per study arm) will be enrolled to achieve the primary endpoint of success at 36 months.

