12.1.1.3. Statistical Methods

For the primary efficacy endpoint, the comparisons of mesh repair to native tissue repair will be based on a two-sided 95% confidence interval for the treatment difference (mesh minus native tissue repair). If the entire confidence interval is above zero, superiority of mesh repair to native tissue repair will be demonstrated. The confidence interval will be calculated based on the pooling of treatment differences across propensity score strata for a binary endpoint, as described in Section 12.2.3 (Propensity Score Methodology).

If any data on the primary efficacy endpoint is missing, multiple imputation will be performed in which the missing values will be imputed five times under a logistic distribution model, using a fully conditional specification that includes the treatment arm and the assessments of the treatment success endpoint at each of 2, 6, 12, 18, and 24 months. As a sensitivity analysis, the comparison of treatments will also be performed using the following methods:

- Tipping point analysis
- Available cases only (i.e., only the subjects for whom the endpoint was assessed)

For the primary safety endpoint, the proportions will be calculated using for the numerator the number of subjects with an endpoint event and for the denominator the number of subjects in the analysis population (ITT and per protocol group). Non-inferiority will be evaluated using a two-sided 90% confidence interval for the treatment difference (mesh minus native tissue repair). If the entire confidence interval is below the margin (10%), non-inferiority will be demonstrated. The confidence interval will be calculated based on the pooling of treatment differences across propensity score strata for a binary endpoint, as described in Section 12.2.3 (Propensity Score Methodology).

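### The plan does not say whether prolapse recurrence, and re-surgery done only for it, count in the co-primary safety endpoint; if they do, the mesh-minus-control difference tends to shift toward mesh

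*Combined protocol and SAP*

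**What the plan says.** Section 12.1.1.1 tests whether the "overall complication rate (i.e. serious adverse device effects and serious procedure-related adverse events) of treatment group is non-inferior to the control group". Section 12.1.1.3 sets a 10% margin and states: "Non-inferiority will be evaluated using a two-sided 90% confidence interval for the treatment difference (mesh minus native tissue repair"). The denominators are the ITT and per-protocol populations. Section 12.3.8.1 applies the same event definition and margin at 12 months.

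In Table 21.7-1 (Section 21.7), the row "Adverse Events related to the study device and/or procedure. Events assessed for reporting shall include but are not limited to" includes "Recurrent prolapse" and revision/re-surgery. The next row, for pelvic-floor-related events, includes pelvic organ prolapse. Section 19.2 lists recurrence and re-surgery as anticipated adverse events.

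Seriousness is defined twice. Section 7.1 uses 21 CFR 803.3, which as stated there has no hospitalization criterion. The SAE definition in Table 21.2-1 adds hospitalization, alongside "medical or surgical intervention to prevent life-threatening illness or injury or permanent impairment to a body structure or a body function".

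Section 11.5 separates the two ideas: a re-intervention "can occur for a medical complication or for prolapse recurrence". Sections 12.3.1 and 12.3.2 test interventions for recurrence for superiority. Sections 12.3.3 and 12.3.4 test interventions for complications for non-inferiority.

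**The concern.** The label says complications, but the definition admits any serious related event, and nothing places recurrence inside or outside it. A woman re-operated for recurrence in the treated segment fails the effectiveness composite through criterion 3. If the same recurrence is judged serious and procedure-related, she is also a safety event.

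The plan expects twice as many effectiveness failures in control as in mesh, so double counting would tend to add more safety events to control. Part of an effectiveness advantage would then be credited to mesh as safety, and the two co-primary results would not be fully separate evidence. With no rule and no endpoint adjudication described (Section 22.1 gives only an internal safety team), coding rests with the sites. Many sites enroll only one arm (Sections 8.2 and 12.2.2), so site coding habits could align with treatment.

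**Working it through.** **The plan's own figure.** Section 12.1.1.2 gives a rate "anticipated to be approximately 14" per cent and states "With type I error of 0.05 and type II error of 0.20 (power 80%), 298 subjects (149 subjects per arm) are needed", with a 10% margin. Taking the 0.05 as one-sided, to match the 90% interval:

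n per arm = 2 × 0.14 × 0.86 × (1.645 + 0.842)² / 0.10² = 148.9, i.e. 149. The stated figure reproduces.

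**Inputs.**
- Margin 10 points and 90% interval: Section 12.1.1.3.
- Failure rates of 30% control and 15% mesh: from the planned success rates of 70% and 85% in Section 12.1.1.2.
- 165 per arm for analysis (Section 8.1) and 207 per arm enrolled (Section 12.1.1.2).
- Assumed: true complication rates, excluding recurrence, of 14% control and 24% mesh, so the true excess equals the margin.
- Assumed, and not in the documents: a share s of composite failures becomes a serious, device- or procedure-related recurrence event. The share is the same in both arms and independent of complications.

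**Formulas.** Each subject counts once, so:
- mesh: pm = 1 − 0.76 × (1 − 0.15s)
- control: pc = 1 − 0.86 × (1 − 0.30s)
- difference: d = pm − pc = 0.10 − (0.258 − 0.114)s = 0.10 − 0.144s
- SE = √[pm(1 − pm)/n + pc(1 − pc)/n]
- P(declare non-inferiority) = Φ[(0.10 − d)/SE − 1.645]

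This is the normal approximation without propensity strata.

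**Example, s = 0.20 and n = 165.** pm = 0.2628, pc = 0.1916, d = 0.0712, SE = 0.0460. Then (0.0288/0.0460) − 1.645 = −1.02, and Φ = 0.154.

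| s | d (points) | P, 165 per arm | P, 207 per arm |
|---|---|---|---|
| 0 | 10.0 | 5.0% | 5.0% |
| 2% | 9.7 | 5.7% | 5.8% |
| 5% | 9.3 | 6.9% | 7.2% |
| 10% | 8.6 | 9% | 10% |
| 20% | 7.1 | 15% | 17% |
| 30% | 5.7 | 23% | 27% |
| 50% | 2.8 | 42% | 49% |
| 2/3 | 0.4 | 59% | 68% |

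**How large s must be.** A full offset needs d = 0. That gives s = 0.10/0.144 = 0.69, or 0.10/0.15 = 0.67 if recurrence and complication events are simply added. Either way it is about two-thirds of all composite failures, i.e. about 20% of control and 10% of mesh subjects. At s = 10% the events are 3% of control and 1.5% of mesh subjects.

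**The case against.** **Entry is not automatic.** A reader might infer from Table 21.7-1 that every recurrence becomes a safety event. The table sets reporting methods and timelines. Relatedness is judged event by event (Sections 21.3 to 21.5), prolapse can also be filed as pelvic-floor-related, and Section 11.5 says re-surgery is typically outpatient. Whether such surgery meets the 21 CFR 803.3 wording is open. All of this stands. However, the relatedness categories are not exclusive, and an event is unrelated to the procedure under Table 21.5-1 only if nothing in its timing points to the procedure. The numerator is therefore undetermined; the documents do not show that recurrence is kept out.

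**Composite failure is wider than recurrence.** Failing one criterion suffices for the composite, whereas Section 11.5 requires both anatomic and symptomatic failure for recurrence. Small values of s are therefore plausible, and the effect is then slight.

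**The estimand.** If the endpoint means all serious related harm, a true difference of 7.1 points lies inside the margin and passing is no error. The 14% planning rate might also already include recurrence. Both are fair: the rise above 5% is measured against a complications-only question. The endpoint's label and Section 11.5 suggest that question, but the plan never says so.

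**Direction.** Device and delivery-device relatedness is assessed in the mesh cohort only (Sections 21.3 and 21.4), which gives mesh events extra routes into the numerator. This may partly offset the shift.

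**Other safeguards.** Surgical and office-based interventions for complications have their own tests, with margins of 4% and 5%. These would show part of a complication excess but do not alter the co-primary decision.

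**Not an isolated case.** A reader might infer that only this endpoint mixes the two ideas. Secondary endpoint 6 pools them too, as do Sections 12.3.5.4 and 12.3.7.

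**Conclusion.** The gap is real: the documents neither include nor exclude recurrence in the co-primary safety numerator. If it is counted, the planned failure rates move the difference toward mesh by about 1.4 points for each 10% of failures that become serious related events, subject to the mesh-only relatedness routes.

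At 165 per arm, with a true complication excess exactly at the margin, the chance of declaring non-inferiority is about 6-7% for s of 2-5% and 9-23% for s of 10-30%, against 5% by design. These figures rest on an assumed s, an equal s in both arms, independence, and 14% being the control rate without recurrence.

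A reader might infer that the design can hide a 10-point mesh excess. The documents do not support that. Across s of 10-30% such an excess would still fail the test 77-91% of the time, and cancelling it needs about two-thirds of all failures to be serious and related. The point is a needed clarification with a two-way report; it does not invalidate the safety endpoint.

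**What to change.** Before the 12-month and 36-month hypothesis tests:

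1. State in Sections 7.1, 12.1.1.1 and 12.3.8.1 whether prolapse recurrence or persistence, and re-surgery solely to treat it, count in the safety numerator. State that complications of such re-surgery count in either case.
2. Report the co-primary non-inferiority result with and without these events, and interpret a safety claim only in light of both.
3. Reconcile the device/procedure and pelvic-floor rows of Table 21.7-1 for prolapse, and the seriousness definitions in Section 7.1 and Table 21.2-1.

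Cost: a flag on adverse-event and re-surgery records and one extra analysis. The reason for intervention is already needed for Sections 12.3.1 to 12.3.4, and no visit or sample-size change is required. Enrollment is complete and the study is open, so redefining the co-primary outright at this stage would be debatable; reporting both counts avoids depending on that choice. The downside is that the safety difference without recurrence may look slightly less favourable to mesh.
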